14.0 Glossary of Abbreviations

Glossary of Abbreviations:

AE	Adverse event
ANCOVA	Analysis of Covariance
ANOVA	Analysis of Variance
ATC	Anatomical Therapeutic Chemical
AUC	Area under the Curve
BQL	Below the quantifiable limit
CI	Confidence Interval
CRF	Case Report Form
CRO	Contract Research Organization
CRP	C-reactive protein
DMC	Data Monitoring Committee
ECG	Electrocardiogram
ECMO	Extra Corporeal Membrane Oxygenation
EWD	Early Withdrawal
FiO ₂	Fraction of Inspired Oxygen
ICH	International Council for Harmonization
ICU	Intensive Care Unit
IMP	Investigational Medicinal Product
ITT	Intention-to-Treat Analysis Set
IXRS	Interactive Web/Voice Response System
LDH	Lactate dehydrogenase
LLOQ	Lower Limit of Quantification
MAR	Missing At Random
MCMC	Markov Chain Monte Carlo
MedDRA	Medical Dictionary for Regulatory Activities
MNAR	Missing Not at Random
PK	Pharmacokinetics
PKS	Pharmacokinetic Analysis Set
PP	Per Protocol Analysis Set
PSO	PRA/ICON system of record
PTs	Preferred Terms
SAP	Statistical Analysis Plan

SAE	Serious Adverse Event
SE	Standard Error
SD	Standard Deviation
SI	System of Unit
SoA	Schedule of Activities
SoC	Standard of Care
SOC	System Organ Class
SpO ₂	Peripheral Capillary Oxygen Saturation
TEAE	Treatment-Emergent Adverse Event
WHODRUG	World Health Organization Drug Dictionary
WNL	WinNonLin

Appendix 1: Estimand Attributes

Table 6: Trial Endpoints and Estimands

Estimand					Analysis	
Variable of Interest	Population	Treatment of Interest	Intercurrent Events	Population-level summary		
Primary Objective:						
- To evaluate the efficacy of C21 versus placebo as add on to SoC on recovery in subjects with COVID-19						
Primary Endpoint:						
- All-cause mortality up to Day 60						
Time to day of death from any cause	Subjects in the ITT analysis set	C21	All other intercurrent events will adopt a treatment policy i.e. the value of the variable of interest is used regardless if an intercurrent event occurs.	Difference in time to all-cause mortality at Day 60 and 95% CI	Stratified log-rank test will be used to compare treatments. Hazard Ratios for death with 95% CIs will be estimated using Cox regression to demonstrate the size of the treatment effect. Subjects who do not have the event before or at Day 60 will be censored at the time of withdrawal/Day 60 follow-up in this analysis. A Kaplan-Meier plot will be produced.	
Sensitivity Analysis of Primary Estimand for the Primary Endpoint:						
1) As primary except population of interest will be the Per Protocol Analysis Set. No missing data will be imputed. 2) As primary except the population level summary will be difference in proportions and 95% CI and estimated difference will be calculated using a weighted estimator based on a logistic regression model. The Standard Error for the difference and the 95% CI will be calculated via the delta method. Subjects with missing data at Day 60 will have data imputed as per Section 10.19.2.						
Supplementary Analysis of Primary Estimand for the Primary Endpoint:						
1) As primary expect the analysis will be restricted to subgroups of interest (see Section 12.5.2.4). No missing data will be imputed.						

Estimand					Analysis	
Variable of Interest	Population	Treatment of Interest	Intercurrent Events	Population-level summary		
Secondary Objective:						
- To evaluate the efficacy of C21 versus placebo as add on to SoC on recovery in subjects with COVID-19						
Key Secondary Endpoint:						
- Time to sustained hospital discharge up to Day 60						
The first occurrence of a score of 2 or below whereafter the score stays ≤ 2 for the remainder of the 60 days trial period	Subjects in the ITT analysis set	C21	
Deaths will not be treated as missing data. They will be considered censored at Day 60 (i.e. worst case) in the analysis.
 
All other intercurrent events will adopt a treatment policy i.e. the value of the variable of interest is used regardless if an intercurrent event occurs.
	Difference in median time to discharge and 95% CI	
Stratified log-rank test. Kaplan-Meier difference in median time to sustained hospital discharge with 95% CIs will be estimated. Subjects who do not have the event before or at Day 60 will be censored at last day in study or day 60 if completing the study.
	
Sensitivity Analysis of Primary Estimand for the Key Secondary Endpoint:						
1) As primary except population of interest will be the Per Protocol Analysis Set						
2) As primary except all re-admissions (COVID-19 and non-COVID-19) will be included.						
3) As primary except missing data will be imputed as per Section 10.19.1.						
Supplementary Analysis of Primary Estimand for the Key Secondary Endpoint:						
1) As primary except the analysis will be restricted to subgroups of interest (see Section 12.5.3.7).						

Estimand					Analysis	
Variable of Interest	Population	Treatment of Interest	Intercurrent Events	Population-level summary		
Secondary Objective:						
- To evaluate the efficacy of C21 versus placebo as add on to SoC on recovery in subjects with COVID-19						
Key Secondary Endpoint:						
- Supplemental oxygen free days up to Day 29						
The number of days between Day 1 and Day 29 with a score of ≤4 on the 8-point ordinal scale and with no documented use of COVID-19 related supplemental oxygen	Subjects in the ITT analysis set	C21	Deaths occurring before Day 29 will not be treated as missing data. They will be considered with -1 days in the analysis. All other intercurrent events will adopt a treatment policy i.e. the value of the variable of interest is used regardless if an intercurrent event occurs.	Difference in median number of days without supplementary oxygen and 95% CI	The Hodges-Lehmann median estimated of the difference in days between treatments with 95% CIs. Missing data will be imputed using multiple imputation (refer to Section 10.19.1)	
Sensitivity Analysis of Primary Estimand for the Key Secondary Endpoint:						
1) As primary except population of interest will be the Per Protocol Analysis Set 2) As primary except the impact of missing data will be explored using a tipping point analysis 3) As primary except missing data will be imputed using Worst Case imputation 4) As primary except the analysis will use an ANOVA model						
Supplementary Analysis of Primary Estimand for the Key Secondary Endpoint:						
1) As primary except the analysis will be restricted to subgroups of interest (see Section 12.5.3.7).						

Estimand					Analysis	
Variable of Interest	Population	Treatment of Interest	Intercurrent Events	Population-level summary		
Secondary Objective:						
- To evaluate the efficacy of C21 versus placebo as add on to SoC on recovery in subjects with COVID-19						
Key Secondary Endpoint:						
- Proportion of subjects free of respiratory failure, defined as an 8-point ordinal scale score ≤ 5 at Day 15						
Proportion of subjects free of respiratory failure, defined as an 8-point ordinal scale score ≤ 5 at Day 15	Subjects in the ITT analysis set	C21	
Deaths occurring before Day 15 will not be treated as missing data. They will be considered as not free of respiratory failure in the analysis.
 
All other intercurrent events will adopt a treatment policy i.e. the value of the variable of interest is used regardless if an intercurrent event occurs.
	Difference in proportions and 95% CI	Estimated difference will be calculated using a weighted estimator based on a logistic regression model. The Standard Error for the difference and the 95% CI will be calculated via the delta method. Missing data due to subject discontinuations from the trial will be imputed using multiple imputation (refer to Section 10.19.1).	
Sensitivity Analysis of Primary Estimand for the Key Secondary Endpoint:						
1) As primary except population of interest will be the Per Protocol Analysis Set						
2) As primary except the impact of missing data will be explored using a tipping point analysis						
3) As primary except missing data will be imputed using Worst Case imputation						
Supplementary Analysis of Primary Estimand for the Key Secondary Endpoint:						
1) As primary except the analysis will be restricted to subgroups of interest (see Section 12.5.3.7).						

Estimand					Analysis
Variable of Interest	Population	Treatment of Interest	Intercurrent Events	Population-level summary	
Secondary Objective:					
- To evaluate the efficacy of C21 versus placebo as add on to SoC on recovery in subjects with COVID-19					
Key Secondary Endpoint:					
- Proportion of subjects discharged from hospital and free of supplemental oxygen at Day 15					
The proportion of subjects with a score of ≤2 on the 8-point ordinal scale and free of COVID-19 related supplemental oxygen use at Day 15	Subjects in the ITT analysis set	C21	
Deaths occurring before Day 15 will not be treated as missing data. They will be considered as not discharged in the analysis.
 
All other intercurrent events will adopt a treatment policy i.e. the value of the variable of interest is used regardless if an intercurrent event occurs.
	Difference in proportions and 95% CI	Estimated difference will be calculated using a weighted estimator based on a logistic regression model. The Standard Error for the difference and the 95% CI will be calculated via the delta method. Missing data will be imputed using multiple imputation (refer to Section 10.19.1)
Sensitivity Analysis of Primary Estimand for the Key Secondary Endpoint:					

 1) As primary except population of interest will be the Per Protocol Analysis Set 2) As primary except the impact of missing data will be explored using a tipping point analysis 3) As primary except missing data will be imputed using Worst Case imputation 					
Supplementary Analysis of Primary Estimand for the Key Secondary Endpoint:					
1) As primary except the analysis will be restricted to subgroups of interest (see Section 12.5.3.7).					

Appendix 2: Logistic Regression for Analysis

As a sensitivity analysis for the primary endpoint and as the primary analysis for select key secondary endpoints, the proportion of responders between treatment groups will be compared using a logistic regression model adjusting for randomized treatment, actual baseline disease severity and region. The Fisher scoring algorithm will be used for maximum likelihood estimation of the regression parameters and the covariance matrix.

The estimated difference between treatments will be calculated using a weighted estimator for the risk difference. The delta method will be used to calculate the standard error for this difference and the associated 95% CI (Ge et al. 2011).

The risk difference is calculated from the fitted logistic regression model as:

$$\text{Difference } (d) = \sum_i \frac{(\hat{P}_{ti} - \hat{P}_{ci})}{n}$$

Where \hat{P}_{ti} and \hat{P}_{ci} are the i^{th} elements of

$$\hat{P}_t = \text{logit}^{-1}(X_t b)$$

$$\hat{P}_c = \text{logit}^{-1}(X_c b)$$

n is the number of subjects in the analysis, b is the maximum likelihood estimate of the regression coefficients from the fitted logistic regression model, X is the covariate matrix of the parameter estimates, X_t is a new covariate matrix from X adjusting the column corresponding to treatment so all subjects are treated, X_c is the new covariate matrix from X adjusting the column corresponding to treatment so all subjects are in the control. \hat{P}_{ti} is the estimated probability of response to treatment for subject i and \hat{P}_{ci} is the estimated probability of response to control for subject i .

The delta method to calculate the standard error and associated CI is as follows:

$$d_t = \frac{(A_t' X_t)}{n}$$

$$d_c = \frac{(A_c' X_c)}{n}$$

$$SE(d) = \sqrt{d_t V d_t' + d_c V d_c' - 2 d_c V d_t'}$$

$$CI \text{ for the estimation} = d \pm z_{(1-\frac{\alpha}{2})} SE(d)$$

Where V is the estimated variance-covariance matrix from the fitted logistic regression and A_t and A_c are the vectors defined as:

$$A_{ti} = \hat{P}_{ti} (1 - \hat{P}_{ti})$$

$$A_{ci} = \hat{P}_{ci} (1 - \hat{P}_{ci})$$

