8.1 Sample Size Considerations

The sample size is based on the all-cause mortality up to Day 60. For the placebo (SOC) group, the proportion of subjects dead at Day 60 is estimated to 10% (Marconi et al., 2021).

With 150 evaluable subjects per trial group, there will be an 80% power to detect a difference between C21 and placebo if the proportion of subjects dead at Day 60 in the C21 group is 2.5% (corresponding to a Hazard Ratio of 0.24). In this calculation a 5% withdrawal rate has been assumed. For the actual detection limit (corresponding to 50% power), if 15 subjects die in the placebo group, significance will be seen if at most 6 subjects die in the C21 group.

This assumes using a 2-sided test at a 5% significance level. Analysis will be by intention-to-treat; thus, all randomized subjects should be accounted for in the statistical evaluation.

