This step will only be performed if missing data does not follow a monotone missing data pattern. This step assumes data is multivariate normally distributed which will not be the case for ordinal data. However, as the number of non-monotone data is expected to be small, the overall impact of this partial imputation step on the analysis at the time point of interest will be small. Subjects who died will be included in this step. Further it is accepted that values of 1 and 2 may be imputed for non-monotone data prior to the observed date of discharge. No adjustments will be made for this as these values are theoretically possible.

2. Missing 8 point ordinal scale data at time point X will be imputed for subjects who did not die using a logistic regression model with the factors of
 - a. Treatment group
 - b. Actual baseline ordinal scale score
 - c. Region (Pooled)
 - d. Age (will not be included in the CLASS statement in the PROC MI)
 - e. Post-baseline daily values of adjusted 8-point ordinal scale up to time point X

Values will be restricted to a minimum value of 1 and a maximum value of 7, as values of 8 will not be present in the data per the previous rules outlined. It is noted that at a time point only values of the ordinal scale recorded at the time point will be possible imputed values. Imputed values may be inconsistent with other data, for example it is possible that an imputed value will be 3 (Hospitalized, not requiring supplemental oxygen - no longer requires ongoing medical care) even if supplemental oxygen is documented on the concomitant medication page.

The number of imputations will depend on the percentage of missing data to be imputed and will range from a minimum of 20 to a maximum of 50. The number of imputations will increase from the minimum of 20 to the maximum of 50 according to the formula:

$$\text{Number of imputations} = 20 + 1.5 * (m)$$

where m is the proportion of missing data, expressed as a percentage. The smallest integer that is greater than or equal to the number will be used (note this will be based on missing data present following step 1 and will not include subjects who died in the calculation)

By default SAS PROC MI, uses the option "LIKELIHOOD=NOAUGMENT" for the computation of maximum likelihood estimates. If the maximum likelihood parameter estimates do not exist or any warning results from this option, the option "LIKELIHOOD=AUGMENT" will be used to get the maximum likelihood estimates.

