12.5.2.2 Primary Analysis

All-cause mortality at Day 60 will be defined as time to day of death from any cause within Day 1 to Day 60 follow-up (refer to Section 10.11). All-cause mortality will be estimated using the Kaplan-Meier methodology where subjects in this analysis without the event will be censored at Day 60 follow-up. Withdrawn subjects without the event will be censored at day of discontinuation (this assumes the censoring is non-informative).

Treatment groups will be compared using a stratified log-rank test adjusting for treatment, actual baseline disease severity and region. The p-value from the stratified log-rank will be presented. The size of the treatment effect will be estimated as a hazard ratio, obtained using a Cox proportional hazards regression model, and the Cox regression model will include a factor for randomized treatment, baseline disease severity and region. The estimated Hazard Ratio comparing C21 to Placebo will be presented together with the corresponding 95% CI (based on Wald test). A Kaplan-Meier plot of time to all-cause mortality will also be produced.

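### Age predicts outcome in the imputation models but is missing from the Day 15 logistic models and the ANOVA/ANCOVA models; adding it would give a modest precision gain

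*SAP*

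**What the plan says.** Age is recorded at screening (Protocol 8.1.1) and summarized as age at consent (SAP 12.2). SAP 10.19.1, step 2, lists it as a continuous predictor for imputing the ordinal score: "Age (will not be included in the CLASS statement in the PROC MI"). SAP 10.19.2 lists it again for imputing Day 60 status. SAP 12.5.2.4 and 12.5.3.7 use it, split at 65 years, as a subgroup factor.

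No analysis model contains it:

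- **Appendix 2** is the main analysis of the two Day 15 key secondary proportions (SAP 12.5.3.4 and 12.5.3.5). It fits a logistic model "adjusting for randomized treatment, actual baseline disease severity and region".
- **The ANOVA** of oxygen-free days (SAP 12.5.3.6) uses the same three terms.
- **The ANCOVAs** for SpO2/FiO2 (SAP 12.5.4) and CRP/LDH (SAP 12.5.5) add only the baseline value of the outcome.
- **For mortality**, SAP 12.5.2.2 tests with a stratified log-rank, and "the Cox regression model will include a factor for randomized treatment, baseline disease severity and region".
- **The Wilcoxon analyses** adjust for nothing.

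Protocol 9.3.2 to 9.3.4 fix the same covariates. Neither document explains the omission or says how strongly age predicts outcome.

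**The concern.** By placing age in both imputation models, the SAP shows that it expects age to carry information about outcome. Randomization is stratified by severity and region only, so a chance age imbalance would go unadjusted. Protocol 5.1 sets no upper age limit outside India, so age may vary widely.

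Appendix 2 averages model-based risks over all subjects. Its target is therefore the marginal difference in proportions named in SAP Appendix 1. Adding a baseline covariate does not alter that target; it only reduces residual variation. The trial was cut from 600 to at most 300 subjects because of recruitment difficulty, so precision available from data already collected is worth having. What is at stake is the width of the Day 15 intervals, and power at the lower end of the testing order.

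**Working it through.** **The plan's own figure.** Inputs are from SAP 8.1. Sample size and power: "With 150 evaluable subjects per trial group, there will be an 80% power to detect a difference between C21 and placebo". Placebo: "the proportion of subjects dead at Day 60 is estimated to 10" per cent. C21: "if the proportion of subjects dead at Day 60 in the C21 group is 2.5" per cent, "corresponding to a Hazard Ratio of 0.24". Test: "This assumes using a 2-sided test at a 5% significance level".

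- Hazard ratio: ln(0.975)/ln(0.90) = 0.240, which agrees.
- Power by the arcsine formula: h = 2·asin(√0.10) − 2·asin(√0.025) = 0.326, and Φ(0.326·√(150/2) − 1.96) = 80.6%. With 5% lost (142.5 per arm) it is 78.6%. The stated 80% is reproduced, although other standard formulas at 150 per arm run from 75.6% to 87.0%.
- Expected deaths: 150 × 0.10 + 150 × 0.025 = 18.75, about 19.

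This calculation uses no covariates, so it says nothing about the value of age. That has to be simulated under assumptions.

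**Day 15 proportions by Appendix 2.** Each simulation fits the logistic model, then takes the standardized difference and its delta-method SE, with and without age, at 150 per arm. The response rates, age effects and age SD are all assumed. An odds ratio of 0.8, 0.67 or 0.5 per 10 years with SD 15 equals a 1.4-, 1.8- or 2.8-fold change per SD (for example, 0.5^1.5 = 0.354, and 1/0.354 = 2.8).

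| Assumed rates | Age effect per SD | Variance reduction | Power without → with age |
|---|---|---|---|
| 65% v 78% | 1.4 | 2% | 0.74 → 0.75 |
| 65% v 78% | 1.8 | 6% | 0.74 → 0.77 |
| 65% v 78% | 2.8 | 16% | 0.73 → 0.80 |
| 55% v 70% | 1.5 | 4% | 79.6 → 80.8% |
| 55% v 70% | 2.0 | 9% | 78.3 → 82.0% |
| 55% v 70% | 3.0 | 17% | 79.2 → 86.3% |

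The 65% v 78% rows use 1,500-2,000 trials each, and type I error stayed at 5%. The 55% v 70% rows use 6,000 runs and assume 25% of subjects at score 6. In terms of sample size, their variance ratios of 0.964, 0.914 and 0.833 equal 300/0.964 = 311, 300/0.914 = 328 and 300/0.833 = 360 subjects.

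Two less favourable settings were run with 3,000 trials each, at 0.8, 0.67 and 0.5 per 10 years:

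- At 65% v 78%, with SD 12 and 80 of 300 subjects capped at age 65 (the Indian limit and enrolment in Protocol 10.5.1), the gains are 0.6, 1.5 and 4.8 points.
- At 85% v 94% with SD 15, the gains are 0.0, 1.2 and 4.5 points.

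**Mortality by Appendix 2** (10% v 2.5%, 12,000 runs). For assumed odds ratios per SD of 1.0, 1.5, 2.0 and 3.0, the variance ratio is 1.01, 1.00, 0.98 and 0.93. Power goes 80.7→80.6, 80.8→81.2, 81.0→82.3 and 80.8→83.9%. The value of 1.01 at no age effect shows how little is lost if age is not prognostic.

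**Stratified log-rank** (1,500 runs, age group as an added factor, 4 to 8 strata). For assumed hazard ratios per SD of 1.0, 1.5, 2.0 and 3.0, power goes 76.9→76.0, 77.3→76.9, 78.0→78.3 and 78.8→78.9%. Simulation error is about √(0.77 × 0.23/1,500) = 1.1 points, so no gain is detectable.

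**Cox model with continuous age.** For the same four hazard ratios, the SE of the log hazard ratio does not fall: 0.593→0.594, 0.592→0.594, 0.593→0.600 and 0.588→0.611. Wald power rises under strong age effects (75.7→80.3% at 3.0) because the estimate becomes an age-conditional hazard ratio further from 1 (0.239→0.226 at 2.0).

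**The case against.** The strongest reply is that this is a preference, not a defect. Protocol and SAP consistently adjust for the two stratification factors, and nothing in that is biased or invalid. That stands. So does the point that an imputation model may be richer than the analysis model. A reader might infer an inconsistency from the two covariate lists, but there is none; the imputation model only shows that the SAP expects age to be informative.

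A second tempting inference is that every analysis gives up precision at no cost. The documents do not support it. Ranks 1 to 3 of the hierarchy (SAP 12.0) are two stratified log-rank tests and a Wilcoxon test. The log-rank cannot take continuous age, the Wilcoxon takes no covariates, and the Cox model would report a different quantity from the one planned. Nor does pooling region to two levels show spare room in the models: Protocol 9.3.1 and SAP 12.0 tie pooling to small strata, and SAP 12.0 already allows factors to be dropped for convergence. With about 19 deaths this matters for the mortality logistic model.

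The gain is also assumption throughout, and the upper end needs nearly a threefold age effect per SD. The Indian age cap narrows the age spread. Finally, the protocol itself fixes the covariates, so the change is a departure from it, and it would follow a mid-trial change of primary endpoint. These points limit the size of the claim and add a documentation step. They do not remove the gain at Day 15, which stays at or above zero in the less favourable settings too.

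**Conclusion.** The point holds for the Appendix 2 analyses of the two Day 15 key secondary endpoints and, by the same reasoning, for the other non-mortality proportions and the ANOVA/ANCOVA models; those last two groups were not simulated. Under assumed age effects of about 1.4- to 3-fold per SD and assumed response rates, the variance of the Day 15 risk difference falls by about 2-17%. Across all settings power rises by about 0 to 7 points. If age is not prognostic, the loss is negligible.

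The change can alter a formal conclusion only at ranks 4 and 5, and only if ranks 1 to 3 are all significant. The reported intervals narrow regardless. For mortality, no gain is shown for the primary log-rank, and the logistic sensitivity analysis gains only about 0-7% of variance for age effects of 1.5 to 3.0 per SD. The recommendation is worth adopting for its low cost; the planned analyses are valid without it.

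**What to change.** Before unblinding:

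- Add age at consent, as a continuous covariate, to the Appendix 2 models for the two Day 15 key secondary endpoints and the other non-mortality proportions in SAP 12.5.4.
- Add it to the ANOVA in SAP 12.5.3.6 and to the ANCOVAs in SAP 12.5.4 and 12.5.5.
- State in SAP 12.0 that, if a model does not converge, age is dropped before the stratification factors.
- List the change in SAP 6.1 as a departure from Protocol 9.3.3 and 9.3.4.
- Leave the stratified log-rank, Cox and Wilcoxon analyses unchanged. Treat age as optional in the mortality logistic sensitivity analysis; if it is added there, also list the departure from Protocol 9.3.2.

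The cost is one more parameter per model, some SAP text and a recorded departure from the protocol's covariate list. No new data are needed.
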